8.7.2 Dose Interruption

A dose interruption is defined as any interruption during the administration (infusion) of a dose of study drug. Dose interruptions are recorded on the Exposure KY1044- IV/Infusion Administration or the Exposure Atezolizumab- IV/Infusion Administration CRF pages in time units of minutes, hours, or days.

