# 2.2 Endpoints

# 2.2.1 Primary Endpoints

# Phase 1

- Safety: Incidence and severity of AEs and SAEs, including changes in laboratory parameters, vital signs and electrocardiograms (ECGs)
- Tolerability: Dose interruptions, reductions and dose intensity
- The incidence of DLTs with KY1044 as single agent during the first 21 days of treatment
- The incidence of DLTs with KY1044 in combination with atezolizumab during the first 21 days of treatment

# Phase 2

• ORR per Response Evaluation Criteria in Solid Tumors Version 1.1 (RECIST 1.1)

10-Nov-2021 Version number: 1

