# 5.2.1 Dosing Regimen

Study treatments	Pharmaceutical form	Route of administration	Dose			Frequency and/or Regimen
			Phase 1	Phase 2 dose assessment	Phase 2	
KY1044	Solution	IV infusion	Escalating doses starting at 0.8 mg	One of two biologically relevant doses	RP2D	Q3W (±3 days)
Atezolizumab	Solution	IV infusion	1200 mg	1200 mg	1200 mg	Q3W (±3 days)

Table 5-1:Dose and Treatment Schedule

Q3W=every three weeks

Patients are to receive KY1044 doses (either as single agent or in combination with atezolizumab) within a 3 days visit window. However, the next dose (as single agent or in combination) may be delayed by up to 7 days to recover from previous Aes.

If doses are not received within this time frame, the dose should be missed and patients should receive the next planned dose according to the schedule on Day 1 of the next cycle. If the patient experiences a related toxicity, the management guidelines provided in Section 5.6 should be followed.

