# 5.3 Treatment Duration

All patients treated with either KY1044 as single agent or in combination with atezolizumab will begin study treatment on Cycle 1 Day 1. Each cycle will consist of 21 days ( $\pm$ 3 days). The next scheduled dose (as single agent or in combination) may be delayed by up to 7 days to recover from previous Aes. If the next dose (as single agent or in combination) cannot be administered within the above mentioned 7-day delay, then the dose should be skipped. Dosing will resume at the scheduled dose or the next lower dose. Dose modifications should follow Section 5.6.

If more than one consecutive dose of KY1044 as single agent or in combination with atezolizumab has to be skipped due to study treatment-related toxicities, then the default position is that IMPs should be permanently discontinued. However, if a patient who misses more than one consecutive dose due to a study treatment-related toxicity experiences clinical benefit, and in the opinion of the Investigator it is in the patient's best interest to remain on study, then the patient may continue treatment after discussion with the Medical Monitor.

A patient may continue treatment with KY1044 as single agent or in combination with atezolizumab within this clinical study, as long as they are continuing to derive benefit from treatment, until the patient experiences unacceptable toxicity or confirmed disease progression per iRECIST. Patients will not be withdrawn from the study due to progressive disease per RECIST 1.1, unless clinically indicated.

Criteria for treatment cessation or patient withdrawal from the study are outlined in Section 8, and management of toxicities is outlined in Section 5.6.

Patients with SD, PR, unconfirmed CR, and unconfirmed progressive disease will continue treatment in additional cycles.

Patients who meet the following criteria will NOT continue treatment in additional cycles:

- Patients who experience unacceptable toxicity.
- Patients with confirmed progressive disease. These patients will enter the Safety follow-up period unless the Investigator considers it to be in the patient's best interest to remain on the study, and after discussion with the Medical Monitor.

• Patients with an unconfirmed progressive disease who show signs of clinical deterioration or toxicity. These patients will enter the Safety follow-up period, and will continue to be followed-up until confirmed progressive disease or initiation of a new treatment.

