# 5.6.2 Follow-up for Toxicities

- The emergence of irAEs may be anticipated based on overall experience in clinical studies with similar immunomodulators.
- An irAE is a clinically important AE of unknown etiology associated with the study • drug exposure. IrAEs are typically low grade and self-limited, often occurring after multiple doses, and most frequently involving the GI tract (diarrhea/colitis), skin (rashes), liver (hepatitis), and endocrine systems (a variety of endocrinopathies) and lung (pneumonitis). Serologic, histologic (tumor sample) and immunological assessments should be performed as deemed appropriate by the Investigator, to verify the immune related nature of the AE, and exclude the neoplastic, infectious or metabolic origin of the AE. Management Algorithms (Table 5-5) have been developed to assist Investigators in assessing and managing the following groups of Aes: Infusion reactions, Hematological, Cardiological, GI, Renal, Pulmonary, Hepatic, Endocrinopathy, Dermatological, Neurological, Ophthalmological, and Rheumatological Aes.
- Patients whose treatment is interrupted or permanently discontinued due to an irAE, AE or clinically significant laboratory value, must be followed-up at least once a week (or more frequently if required by institutional practices, or if clinically indicated) for 4 weeks, and subsequently at approximately 4-week intervals, until resolution or stabilization of the event, whichever comes first. Appropriate clinical experts should be consulted as deemed necessary.
- In case of a suspected irAE, the relevant immunological assessments (eg, rheumatoid factor, anti-deoxyribonucleic acid (DNA) Ab, etc.) should be performed and guidelines as outlined in Table 5-5 (and laboratory assessments Section 6.5.6) should be followed.

All patients must be followed up for irAEs, Aes and SAEs for 90 days following the last dose of KY1044 as single agent or in combination with atezolizumab.

Table 5-5 outlines the follow-up evaluation recommended for selected toxicities. For any irAEs/Aes Grade 1 and/or Grade 2, treatment with KY1044 and atezolizumab (if applicable) should be maintained at the determined dose and schedule, unless otherwise specified in Table 5-5.

10-Nov-2021 Version number: 1

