10.3 Treatments

10.3.1 Extent of Study Drug Exposure

Exposure to study drug will be summarized for all patients in the safety analysis set. Descriptive statistics will be provided for study treatment duration (weeks), the total number of cycles started, number of infusions received, cumulative dose received (mg), absolute dose intensity (mg/week), and relative dose intensity.

The number and percentage of patients with at least 1 dose not administered, dose reduction or increase and at least 1 dose interruption will be presented along with a summary of the reasons for dose not administered, dose reductions and interruptions.

The bar plot of time to treatment will be presented for subject in FAS population.

A listing of study drug exposure will also be created. These data can be found on the Exposure KY1044- IV/Infusion Administration or the Exposure Atezolizumab- IV/Infusion Administration CRF pages.

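### SAP 8.7.2 limits dose interruption to pauses within an infusion, and no SAP table counts doses given late for toxicity

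*SAP*

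**What the plan says.** **Endpoint.** Protocol 2.2.1 lists among the Phase 1 primary endpoints "Tolerability: Dose interruptions, reductions and dose intensity". Section 2.2.2 repeats it as a Phase 2 secondary endpoint. Protocol 9.4.3 says that the number of interruptions and reductions will be summarised.

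**SAP definition.** SAP 8.7.2 reads: "A dose interruption is defined as any interruption during the administration (infusion) of a dose of study drug". It adds that these are recorded "in time units of minutes, hours, or days".

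**SAP tables.** SAP 10.3.1 reports the number and percentage of patients with "at least 1 dose not administered, dose reduction or increase and at least 1 dose interruption", and summarises reasons for doses not administered, reductions and interruptions. SAP 10.7.1 separately tabulates TEAEs that led to interruption of KY1044, of atezolizumab and of either drug. It does not say which meaning of interruption applies.

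**Protocol dosing rules.** Section 5.2.1 sets a visit window of 3 days either side and adds that "the next dose (as single agent or in combination) may be delayed by up to 7 days to recover from previous Aes". Beyond that: "If doses are not received within this time frame, the dose should be missed". Section 5.3 gives the same limit.

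**Protocol usage of the word.** Section 5.6.2 refers to "Patients whose treatment is interrupted or permanently discontinued due to an irAE, AE or clinically significant laboratory value", and 5.6.1 speaks of treatment interruption for concurrent illness. Both mean treatment withheld. Sections 5.2.2 and 5.2.4 use the word for a paused infusion.

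**The concern.** The protocol uses interruption in two senses, and the SAP keeps only the infusion sense. It then provides no other category for a dose that is given, but late. Delay is a routine response to toxicity in this protocol: Table 5-5 names dose delay or holding for many events, and atezolizumab cannot be reduced, so withholding or delay is the only temporary change available for that drug. Table 5-4 even treats certain toxicities that delay dosing by more than 7 days in Cycle 1 as dose limiting.

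At stake is what the Phase 1 tolerability tables can show about a dose level. Two levels could differ in how often toxicity pushes the next dose back by several days and still report the same interruption, skip and reduction rates.

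**Working it through.** The documents give no figure for this point, so there is nothing to reproduce. The check has three parts.

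**1. Where each event is counted under the SAP as written** (8.7.2, 8.7.3, 8.7.5, 10.3.1)

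| Event | Interruption | Not administered | Reduction | Absolute dose intensity |
|---|---|---|---|---|
| Infusion paused, then completed | 1 | 0 | 0 | unchanged |
| Full dose given late, within 7 days | 0 | 0 | 0 | falls |
| Dose skipped after 7 days | 0 | 1 | 0 | falls |
| KY1044 dose lowered | 0 | 0 | 1 | falls |

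The second row is the only one with a schedule or dose change and no count. If the 3-day window and the 7-day limit both run from the planned day, it covers doses 4 to 7 days late.

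**2. What absolute dose intensity shows**

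Inputs: 21-day cycles; SAP 8.7.1 duration in weeks = ((last dose date + 21 − first dose date) + 1)/7; SAP 8.7.5 absolute intensity = cumulative dose / duration. For illustration, take N = 4, 6 or 8 scheduled doses at a constant dose.

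- On time: 21(N − 1) + 21 + 1 = 21N + 1 days.
- One 7-day delay, later doses shifting with it: 21N + 8 days.
- The cumulative dose is the same, so the ratio is (21N + 1)/(21N + 8).

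| N | Ratio, one 7-day delay | Loss |
|---|---|---|
| 4 | 85/92 = 0.924 | 7.6% |
| 6 | 127/134 = 0.948 | 5.2% |
| 8 | 169/176 = 0.960 | 4.0% |

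For comparison, one dose skipped in mid-course gives (N − 1)/N = 0.750, 0.833 and 0.875, and that event is also counted in 10.3.1.

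Upper end, with every later dose 7 days late and each interval re-anchored to 28 days: duration is 28(N − 1) + 22 days, and the ratios are 85/106 = 0.802, 127/162 = 0.784 and 169/218 = 0.775. For N = 6 that is a loss of about 22% with no counted event. If the later doses are instead each 7 days late against a fixed 21-day calendar, the total shift is only 7 days and the ratio is 127/134 = 0.948.

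**3. Relative dose intensity**

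SAP 8.7.5 divides by the starting dose times the number of administrations scheduled within the treatment duration, without saying how that number is counted. After one 7-day delay, for N = 4 / 6 / 8:

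- whole 21-day periods: 1.000 / 1.000 / 1.000
- fractional periods, N × 21/(21N + 8): 0.913 / 0.940 / 0.955
- 21-day calendar slots, N/(N + 1): 0.800 / 0.857 / 0.889

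On the first count the delay does not show at all.

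**The case against.** The strongest case on the other side has five parts.

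- **The endpoint does register delays.** Dose intensity is one of its three named components, and it falls when a late dose is given. This stands. A reader might infer that toxicity delays are missing from the primary tolerability endpoint; the documents do not support that, and the endpoint is primary in Phase 1 only. What remains is that dose intensity mixes delays, skips and reductions and carries neither a patient count nor a reason.
- **The uncounted range is narrow.** Beyond 7 days the dose is skipped and tabulated with its reason, so the longer holds in Table 5-5 would usually be counted. This stands, and it limits the point to late doses that were still given.
- **The SAP 10.7.1 tables may capture holds.** They may rest on an action-taken field of the adverse event page. The CRF is not among the documents, so this is open either way. One cannot say that dose intensity is the only trace, but the SAP should settle the meaning.
- **The protocol never defines dose interruption** and also uses the word for infusions, so the SAP chose one of two usages and did not contradict a definition. This stands. Recording interruptions in days, however, fits poorly with infusions of 30 to 60 minutes (protocol 5.2.2), which suggests that the definition was not fully worked through.
- **Dose decisions do not hang on this table.** Protocol 5.4.5.2 and 5.4.7 base escalation and the RP2D on all relevant safety, exposure and activity data. This stands. The gap is in reporting and need not mislead the SRC.

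**Conclusion.** The point holds in a limited form. Following SAP 8.7.2 and 10.3.1 exactly, a dose given late for toxicity, beyond the 3-day window and within the 7 days allowed, adds zero to the interruption, dose-not-administered and reduction counts. In the exposure tables it shows only through dose intensity: a loss of about 4% to 8% in absolute intensity for one 7-day delay over 8 down to 4 scheduled doses, and possibly none in relative intensity.

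This rests on three assumptions: both limits run from the planned dosing day; later doses shift with the delayed one (if they caught up within the window, the loss would be smaller); and the CRF content is unknown.

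A reader might take the 22% loss as the typical size. It is not: it needs five consecutive maximum delays with re-anchored 28-day intervals. Nor would a trivial infusion pause necessarily pass for toxicity, because SAP 10.3.1 summarises the reasons for interruptions. The change is worth making because the stated rule yields an interruption rate that omits one of the protocol's two meanings of the word, and the repair is cheap.

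**What to change.** Before database lock:

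- **SAP 8.7.2.** Keep infusion interruption as its own category. Add dose delay: a dose given later than the protocol's +3-day window, derived from the dosing dates that 8.7.1 already uses.
- **SAP 10.3.1.** List dose delay beside dose not administered. Give the number and percentage of patients by drug and dose level, with the reason from the CRF or from linked adverse event data where available.
- **SAP 10.7.1.** State that TEAEs leading to interruption include doses delayed or withheld because of the event, and show infusion pauses separately.

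Combining pauses, delays and skips into a single rate is optional; separate categories are enough.

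The cost is one more derived variable, some table shells and a higher reported rate of dose modification. Dosing dates show lateness but not its cause, so reasons may be incomplete if the CRF has no field for them; the table should then say so. No clinical dosing rule is changed.

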8.7.3 Dose Reduction

A dose reduction is defined as any reduction in the dose assigned for infusion and are recorded along with the actual dose administered (infused) on the Exposure KY1044- IV/Infusion Administration. Dose reductions for Atezolizumab are not permitted.

8.7.4 Cumulative Dose Received

Cumulative dose received (mg) is defined as the total amount of study drug received as recorded on the Exposure KY1044- IV/Infusion Administration or the Exposure Atezolizumab- IV/Infusion Administration CRF pages, i.e., the sum of actual dose per administration.

8.7.5 Dose Intensity

Absolute dose intensity (mg/week) is calculated as cumulative dose received (mg) / study treatment duration (weeks).

Relative dose intensity is calculated as the cumulative dose received (mg) / initial planned cumulative dose (mg). Initial planned cumulative dose is calculated as the starting dose (Cycle 1 Day 1 dose) multiplied by the scheduled number of administrations within the study treatment duration.

8.8 Safety Variables

8.8.1 Baseline Signs and Symptoms

Signs and symptoms of the patient's cancer diagnosis and/or comorbidities present prior to Day 1 of study treatment dosing are recorded in the CRF as medical history.

8.8.2 Treatment Emergent Adverse Events

A treatment emergent adverse event (TEAE) is defined as an AE observed after starting administration of the specific treatment. If a patient experiences an event both prior to and after starting administration of a treatment, the event will be considered a TEAE (of the treatment) only if it has worsened in severity (i.e., it is reported with a new start date) after starting administration of the specific treatment, and prior to the start of another treatment (if any) or up to 21 days after the last dose.

8.8.3 Post-Treatment Adverse Events

A post treatment adverse event is defined as an AE with start date being up to 21 days after the last study dose.

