#### Table 6-1:Phase 1 Assessments

Visit name	Screening	Cyc (21 We	cle 1 days; ek 1-3	study 3)	v Day 1	1-21;		Cyc (21 Day We	cle 2 days; s y 22-42; ek 4-6)	tudy		Cyc (21 Day	:le 3 days; 743-6	; study i3; W	eek 7-	9)	Cycle (21 da all Cy to 48 (4 yea	4 ays) and vcles up months urs)	EOT v (up to 21 days after the last study dose)	Safety follow-up visit (90 days after the last study dose)
Day of cycle	-28 to -1		CIDI	C1D2	C1D8	C1D11	C1D15		C2D1	C2D8	C2D15	LUE J	1000	C3D8	C3D11	C3D15	C4D1 and	CXD1		
		pre-dose	post-dose					pre-dose	post-dose			pre-dose	post-dose				pre-dose	post-dose		
Obtain Informed Consent	х																			
Obtain pharmacogenomic informed consent	x																			
Hospital admission a		х																		
IXRS	х	Xp						Хp				Хp					Xp		Х	
Demography	х																			
Inclusion/ exclusion criteria	х	Х																		
Medical History e	х																			
Height	х																			
Weight	х	х						х				х					х		х	
Physical examination d	х	х						х				х					х		х	
Vital signs e	х	х	х	х				x	х			х					х		х	
ECOG performance	х	Х						x				х					х		х	
Oxygen saturation test	х																			

Property of the Sanofi Group - strictly confidential

PAGE 92 OF 217

### Amended Clinical Trial Protocol 07

KY1044/SAR445256-KY1044-CT01/TCD17370 - alomfilimab

10-Nov-2021 Version number: 1

Visit name	Screening	Cyc (21 We	cle 1 days; ek 1-3	study 3)	v Day I	1-21;		Cyc (21 Day We	cle 2 days; s y 22-42 ek 4-6)	tudy ;		Cyc (21 Day	cle 3 days y 43-6	; study 53; W	eek 7-	9)	Cycle (21 da all Cy to 48 (4 yea	e 4 ays) and vcles up months urs)	EOT v (up to 21 days after the last study dose)	Safety follow-up visit (90 days after the last study dose)
Day of cycle	-28 to -1			C1D2	C1D8	CIDII	CID15		C2D1	C2D8	C2D15		CODI	C3D8	C3D11	C3D15	C4D1 and CXD1			
		pre-dose	post-dose					pre-dose	post-dose			pre-dose	post-dose				pre-dose	post-dose		
Cardiac markers f	x																			
12-Lead ECG g	x	х	х									х	x						х	
Review AE	x	х	х	x	х	х	x	х	х	х	х	х	x	Х	х	х	х	Х	x	х
Review Concomitant Medications	х	х						Х				х					х		x	х
Hematology	х	X h		X h	X h		X h	X h		X h	X h	X h		X h			X h		х	

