#### 9.4.3 Safety Analysis

The Phase 1 primary and Phase 2 secondary safety endpoints include:

- Safety: Incidence and severity of AEs and SAEs, including changes in laboratory parameters, vital signs and ECGs
- Tolerability: Dose interruptions, reductions and dose intensity

For Phase 1, the primary endpoints will also include:

- The incidence of DLTs with KY1044 as single agent during the first 21 days of treatment
- The incidence of DLTs with KY1044 in combination with atezolizumab during the first 21 days of treatment

All AEs in the clinical trial database will be coded according to the Medical Dictionary for Regulatory Activities (MedDRA) Version 21.0 or higher, which will be used to summarize AEs by primary system organ class (SOC) and preferred term (PT). All AEs will be displayed in listings.

A treatment emergent adverse event (TEAE) is defined as an AE observed after starting administration of the specific treatment. If a patient experiences an event both prior to and after starting administration of a treatment, the event will be considered a TEAE (of the treatment) only if it has worsened in severity (ie, it is reported with a new start date) after starting administration of the specific treatment, and prior to the start of another treatment, if any. All TEAEs collected during the investigational period will be summarized.

Treatment-related AEs/SAEs coded by primary SOC and PT will be summarized in those receiving at least one infusion of KY1044.

Additional summaries by severity of AEs/SAEs will also be produced.

Actual and change from baseline data for vital signs and ECG parameters will be reported using summary statistics.

When relevant, for laboratory variables, descriptive statistics for results and changes from baseline will be provided during the on-treatment period. These analyses will be performed using local measurements for laboratory variables. Clinical laboratory results will be graded according to NCI CTCAE version 5.0, when applicable. Number (%) of participants with laboratory abnormalities (all grades and by grade) using the worst grade during on-treatment period will be provided for the all-treated population.

When the NCI CTCAE version 5.0 scale is not applicable, the number of participants with laboratory abnormality out-of-normal laboratory range value will be displayed.

The number of dose interruption, reductions and incidence of DLTs will be summarized.

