8.7.1 Study Treatment Duration

Study treatment duration (weeks) for each study drug separately is defined as ((last dose date+21 days – first dose date)+1)/7. For patients in the combination arm, an additional duration of study treatment will be calculated using the same formula but which takes the latest KY1044 or Atezolizumab administration for the last dose date, and the earliest of either drug for the first dose date.

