10.7.2 Deaths and Serious Adverse Events

A summary of TEAEs, including the number of events reported, the number and percentage of patients reporting at least one SAE and deaths will be presented.

The following summaries of AEs will be provided for each treatment group by MedDRA primary SOC and PT:

- Serious TEAEs
- Serious TEAEs related to KY1044
- Serious TEAEs related to Atezolizumab
- Serious TEAEs of special interest
- TEAEs with an outcome of death
- TEAEs related to KY1044 with an outcome of death
- Post treatment AEs with an outcome of death

The listings of all SAEs and AEs with outcome of death will be provided. A separate listing of all deaths during treatment will be provided.

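### SAP 8.8.3 gives post-treatment AEs the same 21-day limit as TEAEs, so the planned table of fatal post-treatment AEs largely repeats fatal TEAEs and cannot hold an AE starting on days 22 to 90

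*SAP*

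**What the plan says.** SAP 8.8.3 is one sentence: "A post treatment adverse event is defined as an AE with start date being up to 21 days after the last study dose". It gives no lower limit, and no other section redefines the class.

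SAP 8.8.2 first calls any AE seen after a treatment has started a TEAE, with no end date. Its second sentence deals with events already present before treatment. These count only if they worsen after treatment starts and "prior to the start of another treatment (if any) or up to 21 days after the last dose". The matching text in protocol 9.4.3 reads "prior to the start of another treatment, if any. All TEAEs collected during the investigational period will be summarized" and has no 21-day limit.

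SAP 10.7.2 uses the post-treatment class once, for a summary by SOC and PT of "Post treatment AEs with an outcome of death". A separate summary covers TEAEs with a fatal outcome. An unbulleted overview, introduced as a summary of TEAEs, says that "the number and percentage of patients reporting at least one SAE and deaths will be presented". On listings, 10.7.2 says: "The listings of all SAEs and AEs with outcome of death will be provided". SAP 10.7.1 bases its tables on TEAEs and ends by listing every AE on the CRF, treatment-emergent or not.

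Protocol 7.1 and 5.6.2 collect and follow AEs to 90 days after the last dose. Protocol 7.1.7 requires deaths and fatal AEs in that period to be reported as SAEs.

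**The concern.** A reader of a safety report takes a post-treatment table to show events that began after the treatment-emergent window closed. Here the two classes close on the same day. A table presented as the complement of the fatal TEAE table would mostly show the same events again, and would be silent on the later part of follow-up.

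That later part is of interest on the protocol's own terms. Protocol 7.2.2 expects a KY1044 half-life of about 3 weeks, so day 21 is only about one half-life after the last dose, and drug-related onset after it is plausible. AE and SAE incidence is a Phase 1 primary and a Phase 2 secondary endpoint. What is at stake is the accuracy of descriptive safety tables; no test or dose decision rests on this class.

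**Working it through.** No figure in the plan needs reproducing, so the check compares windows. Days are counted from the last dose.

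**Post-treatment class (SAP 8.8.3).** The upper limit is day 21. The lower limit is either the last dose (narrow reading) or absent (literal reading, which also admits on-treatment AEs). Days 22 to 90 number 90 − 21 = 69, and the class covers 0 of them on both readings.

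**TEAE class (SAP 8.8.2).** The wording allows at least four readings:

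| Reading of 8.8.2 | New-onset AE, from last dose to day 21 | AE starting on days 22 to 90 |
|---|---|---|
| Day 21 caps all TEAEs | TEAE, so full overlap with 8.8.3 | Not a TEAE |
| Window ends at day 21 or at the start of another treatment, whichever is first | TEAE unless another treatment has started | Not a TEAE |
| Limit applies only to worsened pre-existing events | TEAE, so full overlap | TEAE if new-onset; not if a worsened pre-existing event |
| Meeting either limb is enough | TEAE, so full overlap | TEAE if no other treatment has started |

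Two examples show the effect. An AE on day 15, after another treatment began on day 10, is in the post-treatment class on every row but is not a TEAE on the second row. An AE on day 40 in a patient with no further treatment is never in the post-treatment class. It is a TEAE on the fourth row and, if new-onset, on the third.

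**Fatal-AE table (10.7.2).** Membership depends on AE onset, not date of death. An AE starting on day 15 and fatal on day 60 is post-treatment under 8.8.3. Unless another treatment had already started, it is also a fatal TEAE and appears in both tables. A fatal AE starting on day 40 cannot enter the post-treatment table on any reading.

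**Other summaries.** SAP 10.7.1 has 21 bulleted summaries: 20 name TEAEs, and the one on immune-related AEs is TEAE-based only through the section's opening statement. SAP 10.7.2 has 7: 6 name TEAEs and 1 uses the post-treatment class. The total is 21 + 7 = 28. On the first two rows, none of the 28 shows an AE starting on days 22 to 90. On the last two rows, some or all such AEs reach the TEAE tables. Whether the death count in the 10.7.2 overview is limited by AE onset is not stated.

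**The case against.** The strongest reply is that this is probably a slip for more than 21 days, that its certain effect is one descriptive table, and that nothing is lost because every AE, SAE and fatal AE is listed. Most of that stands. The documents do not say that it is a slip, however, and programmers will code what is written. A listing does not correct a summary table whose title and content disagree.

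Several stronger readings are tempting, and the documents do not support them:

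- A reader might infer that every AE in the post-treatment class is also a TEAE, or that no bulleted summary can show an AE from days 22 to 90. Each holds on some readings of 8.8.2 and fails on others, because of the reference to another treatment.
- A reader might infer from SAP 8.7.1 ("Study treatment duration (weeks) for each study drug separately is defined as ((last dose date+21 days") that the SAP itself places the class within treatment. That is an exposure variable, used as the denominator for absolute dose intensity in 8.7.5; it does not define an AE period.
- A reader might take the end-of-treatment visit window in protocol Table 6-1 ("up to 21 days after the last study dose") as a second anchor. That is visit scheduling, and protocol 8.2 also allows the visit within 21 days of the decision to stop, so it need not fall by day 21 after the last dose.

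**Conclusion.** SAP 8.8.3 is wrong as written. It does not define a class distinct from TEAEs, and on any reading it excludes AEs starting on 69 of the 90 follow-up days. The fatal post-treatment table in 10.7.2 is therefore wrong: it largely repeats fatal TEAEs and holds no fatal AE with onset after day 21. This needs no assumption beyond the text.

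The wider effect is conditional. If day 21 caps all TEAEs, AEs from days 22 to 90 appear in none of the 28 bulleted summaries. If it does not, two programmers could reach different TEAE counts.

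The day count shows coverage, not events; the documents give no rate of late-onset AEs, so the number affected cannot be stated. Evaluation of Cycle 1 DLTs does not use this class, and no hypothesis is tested. The point should be fixed before the safety tables are produced, but it does not threaten the trial's conclusions.

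**What to change.** In SAP 8.8.2, state one upper limit that applies to all TEAEs, new-onset and worsened. Say whether the start of another treatment ends the window and, if it does, which class later AEs fall in. Then choose one of two options:

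1. Keep last dose + 21 days for TEAEs, and record that protocol 9.4.3 has no such limit. Define post-treatment AEs in 8.8.3 as all AEs starting after the TEAE window closes and up to the 90-day safety follow-up. Produce the fatal post-treatment table in 10.7.2 on that window.
2. Run the TEAE window to the 90-day safety follow-up, and delete 8.8.3 and its bullet in 10.7.2.

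Once the role of another treatment is settled, either option leaves no overlap and no gap before day 90. The cost is wording in two SAP sections and one table corrected or deleted. No new data are needed, because AEs are already collected to day 90. Further post-treatment tables, such as SAEs or AEs by grade, are optional.
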